### **3.4 Time Schedule**

The trial is planned to start in October 2016 and complete before July 2019, with about 10 patients enrolled per month. Patients will be followed up for one month after surgery to monitor postoperative complication.

### **3.5 Statistical Analysis**

To decide whether the localization accuracy, radiation exposure and complication rate in the two groups are significantly different, three tests are used: 1) independent samples  $t$  tests for continuous variables that were normally distributed; 2)  $X^2$  tests for categorical variables, and 3.) Mann-Whitney U test for continuous variables that were not normally distributed.

Because of the possibility of patients withdraw, intention-to-treatment (ITT) analysis and efficacy analysis are both performed. ITT analysis is conducted for participants who received lung nodule localization and subsequent surgery. Efficacy analysis is only performed for patients who received lung nodule localization according to their assignment. All statistical analyses are two-tailed with a significance level of 0.05.

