### **3 STUDY DESIGN**

The study is designed to be a prospective, randomized, non-inferiority clinical trial comparing template-guided to CT-guided peripheral small lung nodule localization. The feasibility of template-guided lung nodule localization has already been confirmed in our previous study. The study is a phase II clinical trial and further examines the safety and efficacy of template-guided lung nodule localization.

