#### **3.2 Sample Size Calculation**

The study was designed to confirm the non-inferiority of template-guided lung nodule localization compared to CT-guided lung nodule localization in terms of localization accuracy. And the accuracy of lung nodule localization was quantified by the localizer deviation between the localization and the center of the target nodule.

The expected difference of localizer deviation between CT- and template-guided group was 3.5mm according to priori study. Deviation of 5mm is set as non-inferiority margin. We needed to randomize 140 patients (70 each group) to give 90% power with one-sided alpha of 0.05. To allow for some dropouts, inclusion of 100 patients per group is planned.

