### **3.3 Interim Analysis**

An interim-analysis is performed on the primary and secondary outcomes when 40% of patients have been randomized. The interim-analysis is performed by an independent statistician, blinded for the treatment allocation. The data monitoring committee will have unblinded access to all data and will discuss the results of the interim-analysis in a joint meeting, and report to the ethics committee. Based on the results of interim-analysis, principal investigator decides whether the trial continues or not. The trial will be ended if the localizer deviation is significantly larger in template-guided lung nodule localization than CT-guided localization, and no benefit is obtained for patients undergoing template-guided lung nodule localization. Otherwise, the trial will be continued.

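### The trial is designed and sized for non-inferiority with a 5 mm margin, but section 3.5 only tests localizer deviation for a difference from zero

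*Combined protocol and SAP*

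**What the plan says.** Section 3 sets the design: "The study is designed to be a prospective, randomized, non-inferiority clinical trial". Section 3.2 gives the purpose, "The study was designed to confirm the non-inferiority of template-guided lung nodule localization", on localizer deviation, which section 2.2.1 makes the primary outcome. Section 3.2 then sets the margin, "Deviation of 5mm is set as non-inferiority margin", and the size, "We needed to randomize 140 patients (70 each group) to give 90% power with one-sided alpha of 0.05", and raises the planned number to 100 per group for dropouts. On the expected effect it says only: "The expected difference of localizer deviation between CT- and template-guided group was 3.5mm according to priori study". It does not say which method is expected to be worse, and it gives no SD.

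Section 3.5 is the only description of the final analysis. It opens: "To decide whether the localization accuracy, radiation exposure and complication rate in the two groups are significantly different, three tests are used". The tests are the independent-samples t test, the chi-square test and the Mann-Whitney U test, chosen by type of variable and normality. It ends: "All statistical analyses are two-tailed with a significance level of 0.05".

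The only other rule on deviation is the interim stop in section 3.3: "The trial will be ended if the localizer deviation is significantly larger in template-guided lung nodule localization than CT-guided localization". That rule also requires that no benefit is seen for template patients.

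**The concern.** A non-inferiority claim means rejecting the hypothesis that the template is worse than CT guidance by 5 mm or more. Section 3.5 instead tests the hypothesis of zero difference. The two questions have different answers: a non-significant difference does not show that the deficit is under 5 mm, and a significant one does not show that it exceeds 5 mm.

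Section 3.5 names localization accuracy explicitly, so it cannot be read as covering the secondary outcomes only. Its last sentence covers all analyses, so it also contradicts the one-sided alpha of 0.05 in section 3.2.

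At stake is the trial's one confirmatory conclusion. The plan does not say whether p<0.05 would mean failure or p>0.05 success, so the criterion could be settled after the data are seen. Two misreadings are possible: a template within the margin is reported only as significantly worse, or p>0.05 is taken as non-inferiority when the true deficit equals the margin.

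**Working it through.** **Sections compared**

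| Item | Sections 3 and 3.2 | Section 3.5 |
|---|---|---|
| Question | Is the template non-inferior? | Do the groups differ? |
| Reference value | 5 mm | 0 mm (implicit) |
| Alpha | one-sided 0.05 | two-tailed 0.05 |
| Confidence limit compared with 5 mm | implied by the margin | none |

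The margin appears only in section 3.2. The mismatch follows from the text alone; the rest of this check measures its size.

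**Inputs.** From section 3.2: margin 5 mm, expected difference 3.5 mm, 70 per group (100 planned), 90% power, one-sided alpha 0.05. Assumed: the SD and the sign of the 3.5 mm. Differences (d) are template minus CT, so positive values mean the template is worse.

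**The plan's own figure.** The 70 per group cannot be reproduced without an SD. Solving backwards:

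SD = (5 − d) × √(70/2) / (1.645 + 1.282)

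- d = +3.5 mm: 1.5 × 5.916 / 2.927 = 3.03 mm
- d = 0: 5 × 5.916 / 2.927 = 10.1 mm
- d = −3.5 mm: 8.5 × 5.916 / 2.927 = 17.2 mm

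**Case A: the template is truly 3.5 mm worse.** At SD 3.03 mm and 70 per group, SE = 3.03 × √(2/70) = 0.512 mm.

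- Significantly worse if the observed difference exceeds 1.977 × 0.512 = 1.01 mm.
- Non-inferior at one-sided 0.05 if it is below 5 − 1.656 × 0.512 = 4.15 mm.

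Observed differences from about 1.0 to 4.2 mm meet both conditions. Simulated probability of both (400,000 runs, equal-variance t, SD estimated in each run):

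| SD (mm) | 70 per group | 100 per group |
|---|---|---|
| 3.03 | 90% | 97% |
| 5 | 53% | 68% |
| 7 | 19% | 39% |
| 10 | 0% | 1% |

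The overlap exists only if SD is below 5 / [(t₀.₉₇₅ + t₀.₉₅) × √(2/n)]: 8.1 mm at 70 per group and 9.8 mm at 100.

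**Case B: the true deficit is 5 mm, at the margin.** A correct non-inferiority test at one-sided 0.05 would wrongly succeed in 5% of trials. Probability that the section 3.5 test gives p>0.05:

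| SD (mm) | 70 per group | 100 per group |
|---|---|---|
| 3.03 | about 0% | about 0% |
| 7 | 1.3% | 0.1% |
| 10.1 | 17% | 6% |
| 17.2 | 60% | 47% |

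Section 1.3.1 reports a median deviation of 10.0 mm in the feasibility trial. An SD of 17.2 mm is large beside that and is best treated as an upper limit.

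A and B are alternatives and do not add up: A needs a small SD and B a large one.

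**The case against.** The strongest reply is that sections 3.2 and 3.5 belong together: the first supplies hypothesis, margin and alpha, the second lists tests for several outcomes, and the link was left unwritten. A t test also yields a confidence interval that could be set against 5 mm, and nothing in the plan says that p>0.05 means success. This has some force, and the two misreadings are indeed hypothetical. But the plan does not ask for an interval, choose 90% or 95%, or compare anything with 5 mm, and the two-tailed sentence contradicts section 3.2. In the Mann-Whitney branch, a p-value against zero cannot be compared with a margin at all. The median in section 1.3.1 makes that branch possible, but does not prove skewness.

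The objections to the size largely stand:

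- The 90% in case A follows from back-solving the SD at 90% power: at SD 3.03 mm nearly every non-inferior trial is also significantly worse. An SD of 3.03 mm may be small beside a 10.0 mm median; at SD 5 mm the figure falls to 53% or 68%.
- Significantly worse yet within the margin is not a logical contradiction. The fault is that the plan would report only the first half.
- In case B, at SD 10.1 mm and 100 per group, about 6% is barely above the 5% of a proper test. At SD 7 mm the planned test is the stricter one. The excess is material only with heavy loss or a larger SD.
- The interim rule has a second condition, and a rule for stopping for harm need not use the margin. It shows only that the missing comparison is not made there either.

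None of this supplies a non-inferiority test.

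**Conclusion.** The point holds and must be fixed before analysis. No planned analysis tests the stated primary hypothesis, and sections 3.2 and 3.5 conflict on sidedness. Confidence is high, because this rests on the text and not on any assumed SD.

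The practical size is conditional. If the template is 3.5 mm worse and the SD is between 3.03 and 7 mm, 19% to 90% of trials at 70 per group, or 39% to 97% at 100, would be non-inferior yet appear under section 3.5 only as significantly worse. If the SD is near 10 mm or more, the risk is instead that a true 5 mm deficit passes as no significant difference. These figures assume normally distributed deviations with equal variances.

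**What to change.** In section 3.5:

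1. State the primary null hypothesis: mean localizer deviation, template minus CT, is 5 mm or more.
2. Estimate that difference with a two-sided 90% Welch confidence interval, which matches the one-sided 0.05 of section 3.2. Declare non-inferiority only if the upper limit is below 5 mm.
3. Exempt this analysis from the two-tailed sentence.
4. If deviations are skewed, use a bootstrap 90% interval for the same mean difference, not a Mann-Whitney p-value. A Hodges-Lehmann interval is an alternative, but it estimates a shift, not a mean difference, so the choice must be made in advance.
5. Keep the difference tests for secondary outcomes, and test superiority on deviation only after non-inferiority is shown.
6. Say whether non-inferiority must hold in the ITT set, the efficacy set or both. Section 5.2 sends some template patients to CT guidance, so the two sets could disagree.

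The cost is a few sentences, with the same data and no extra patients at one-sided 0.05.

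If the sponsor prefers a two-sided 95% interval (one-sided 0.025), section 3.2 must be restated. With SD 3.03 mm and a true +3.5 mm, power is about 83% at 70 per group and 94% at 100. For 90% power, n = 2 × [3.03 × (1.960 + 1.282) / 1.5]² = 85.8, so 86 evaluable per group. The planned 100 then tolerates 14% dropout, less than half the 30% allowed by going from 70 to 100.

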## **PROTOCOL SUMMARY**

**Title:** Application of 3D printing technique in small pulmonary nodule localization: A Prospective, Randomized, Controlled, Non-inferiority Trial.

**Objective:** To evaluate the accuracy and safety of template-guided lung nodule localization compared to standard computed tomography (CT)-guided localization.

**Participants:** Surgical candidates with solitary pulmonary nodule <2 cm will be approached prior to scheduled lung resection. The necessity of preoperative nodule localization would also be evaluated by the patient's operating surgeon in charge. After acquiring patients' consent to participate into the study, enrolled patients will be randomized into the CT- or template-guided group using a previously generated random table. According to priori study, each group would have a sample size of 100 participants.

[figure not shown]
**Number of site:** This is a single-center trial and all participants would be recruited in Shanghai Pulmonary Hospital.

**Description of Intervention:** The three-dimensional printed, navigational template was created to guide percutaneous lung nodule localization. Its utility has been tested in previous feasibility trial.

**Estimated Study Duration:** From 01-10-2016 to 01-07-2019.

**Estimated Time to Complete Enrollment:** From 01-10-2016 to 01-06-2019.

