## **1.3 Potential Risks and Benefits**

### **1.3.1 Potential Risks**

The mechanism of template-guided lung nodule localization is the same as conventional CT-guided localization. Therefore, complications related to percutaneous lung nodule localization such as pain, pulmonary hemorrhage, pneumothorax, hemoptysis and so on, likely occur. Most of these complication is non-significant and do not need special intervention.

For patient assigned to receive templated-guided nodule localization, the most worrying concern is the accuracy of lung nodule localization. Firstly, the previous feasibility trial has confirmed the precision of the navigational template, with 10.0 mm of the median localizer deviation and no occurrence of severe complications in template-guided localization. Secondly, for the sake of safety of participants in this trial, patients would receive CT scan to confirm the accuracy of the template-guided lung nodule localization after template placement but before localizer insertion.

Regarding to the concern of infection, the entire template was sterilized by UV irradiation for 30 minutes and the area adjacent to puncture point was sterilized using iodine. And the metal introducer sheath, through which the localizer was introduced, was sterilized using autoclave sterilizer. And infection of the puncture site was not found in our previous study. Additionally, as the template is made of nylon (PA3200), patients with a history of nylon allergy should not receive template-guided localization.

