## **2 OBJECTIVES**

### **2.1 Study Objectives**

To evaluate the safety and accuracy of navigational template-guided method in percutaneous lung nodule localization.

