### **2.2.2 Secondary outcome**

The secondary outcome includes procedural length, radiation exposure dosage and related complication rate.

In order to facilitate the process of data collection, the procedural length of nodule localization was inferred from CT scanning parameter. The time length of nodule localization is calculated from patients receiving the initial CT scan to patients receiving the last CT scan for complication evaluation. And, the radiation exposure dosage (dose-length-product) is directly collected from monitor screen after the last CT scanning. The complication related to percutaneous lung nodule localization mainly includes pneumothorax, pulmonary hemorrhage and hemoptysis during the time of waiting for surgery. The occurrence of pneumothorax and pulmonary hemorrhage is evaluated by CT scanning immediately after localizer release.

Additionally, localizer dislodgement rate and the margin distance reported on frozen analysis are also compared between patients undergoing CT-guided nodule localization and patients receiving template-guided nodule localization.

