## **5.2 Experiment Group**

Patients in the template-guided group underwent template-guided percutaneous lung nodule localization using a hookwire. After template placement and prior to hookwire insertion, an initial CT scan is obtained to pre-evaluate the accuracy of nodule localization. If the deviation is less than 2 cm on the initial CT scan, the hookwire is inserted, and the localizer is deployed. However, if the deviation  $>2$  cm based on the pre-evaluation on the initial CT scan, patients would receive conventional CT-guided localization.

After successful nodule localization, the CT scan is immediately obtained in order to evaluate the incidence and severity of the pneumothorax and hemorrhage in both groups. Afterwards, patients are wheeled back to the unit where they wait for the scheduled surgery. During the waiting period, patients are closely observed by nurses, and any occurrence of dyspnea and hemoptysis are detailly recorded.

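### Safety is a stated objective, but the only planned complication analysis is a chi-square test for a difference, with no confidence interval and no analysis of the severity recorded on CT

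*Combined protocol and SAP*

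**What the plan says.** The Protocol Summary gives the objective as "To evaluate the accuracy and safety of template-guided lung nodule localization compared to standard computed tomography (CT)-guided localization", and section 2.1 repeats it: "To evaluate the safety and accuracy of navigational template-guided method in percutaneous lung nodule localization".

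The safety outcome is secondary. Section 2.2.2 states: "The secondary outcome includes procedural length, radiation exposure dosage and related complication rate". It then lists the components: "The complication related to percutaneous lung nodule localization mainly includes pneumothorax, pulmonary hemorrhage and hemoptysis during the time of waiting for surgery".

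Section 5.2 requires a CT scan directly after successful localization to "evaluate the incidence and severity of the pneumothorax and hemorrhage in both groups". No section gives a grading scale or says how severity will be compared.

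Section 3.5 holds the whole analysis: "To decide whether the localization accuracy, radiation exposure and complication rate in the two groups are significantly different, three tests are used". For complications this means chi-square "tests for categorical variables", two-tailed at 0.05. No confidence interval, safety margin or rule for reaching a safety conclusion appears in the documents.

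Section 1.3.1 says of the expected complications: "Most of these complication is non-significant and do not need special intervention". Section 3.2 bases the sample size on localizer deviation only: 70 per group, raised to 100 for dropouts.

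**The concern.** A difference test answers whether the data show that the arms differ. A safety objective asks how large an excess of complications with the template the data can rule out. In a trial sized for another outcome, failing to find a difference says little about the second question, and the plan supplies nothing else with which to answer it.

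Severity adds to this. By the protocol's own account most events are minor, so an incidence comparison will mostly reflect minor events. Severity is the information that would show whether the more important ones differ. It is to be assessed, yet no analysis of it is named.

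At stake is the wording of the safety conclusion. If the chi-square test is not significant, the report has no planned basis for saying how much worse the template could be.

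**Working it through.** **Inputs from the documents.** Two arms; 70 per group required and 100 planned (section 3.2); chi-square, two-tailed, 0.05 (section 3.5). The documents give no complication rate for either arm, so every rate below is an assumption and a range is shown. I take the chi-square test as the uncorrected Pearson form, which the plan does not specify.

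**The plan's own figure.** There is none for safety. The 70 per group is for the 5 mm margin on localizer deviation, with 90% power and one-sided alpha 0.05. It cannot be reproduced because no standard deviation is given. With a true difference of zero it implies 5 / [(1.645 + 1.282) × √(2/70)] = 10.1 mm. This has no bearing on complications.

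**1. Power of the planned test.** With n per arm, rates p1 and p2, and mean rate p̄:

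power ≈ Φ{ [|p2 − p1| − 1.96 √(2p̄(1−p̄)/n)] / √([p1(1−p1) + p2(1−p2)]/n) }

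For 20% v 30%:

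- n = 100: (0.100 − 1.96 × 0.0612) / 0.0608 = −0.33, so power is 0.37.
- n = 70: (0.100 − 1.96 × 0.0732) / 0.0727 = −0.60, so power is 0.275.

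Exact binomial enumeration, counting only rejections that show harm from the template, gives 37.1% and 28.0%. The rise is therefore missed 63% and 72% of the time. Other assumed 10-point rises, also by enumeration:

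| CT v template, any complication | Power, 100 per group | Power, 70 per group |
|---|---|---|
| 10% v 20% | 52% | 38% |
| 20% v 30% | 37% | 28% |
| 30% v 40% | 32% | 24% |

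**2. What a null result would leave open.** The Newcombe interval combines the Wilson limits (l, u) of the two arms. The upper limit is d + √[(u1 − p1)² + (p2 − l2)²], and the lower limit is formed in the same way.

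- 20/100 in each arm: Wilson limits 0.133 and 0.289, so the half-width is √(0.089² + 0.067²) = 0.111. The interval is −11 to +11 points.
- 14/70 in each arm: Wilson limits 0.123 and 0.308, so the half-width is √(0.108² + 0.077²) = 0.133. The interval is −13 to +13 points.
- 30/100 with the template v 25/100 with CT: p = 0.43, interval −7 to +17 points.

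**3. Rarer events.** Suppose 6/100 v 1/100. Chi-square = 200 × (6×99 − 1×94)² / (100 × 100 × 7 × 193) = 3.70, p = 0.054 (Fisher 0.12), with an interval of −0.5 to +11.5 points. The p value alone would hide how large the excess could be.

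**4. Scale of a true safety comparison.** Purely as an illustration, excluding a 10-point excess when both true rates are 20%, at one-sided 0.025 and 80% power, needs (1.960 + 0.842)² × 2 × 0.20 × 0.80 / 0.10² ≈ 252 per arm. Rates of 10% and 30% give 142 and 330. The plan states no such margin and none is proposed here.

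**The case against.** Much of the case on the other side stands.

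- **No rule equates p>0.05 with safety.** A reader might infer from section 3.5 that a non-significant result will be reported as safe. The documents do not say so. Section 1.3.2 expects fewer complications with the template, so the test may be meant to show a benefit. The plan is silent on what follows if no difference is found.
- **Pooling is not stated.** A reader might infer one composite rate in which fewer trivial events cancel more serious ones. Section 2.2.2 lists types and does not say whether they are pooled. An example such as 20% overall in both arms with 2% v 8% serious needs both pooling and a matching fall in minor-only events from 18% to 12%. Testing by type would weaken this argument, although severity within a type would still have no analysis.
- **Severity is not recorded for everything.** Section 5.2 covers pneumothorax and hemorrhage on CT only. No section shows that the need for intervention is a recorded item.
- **Serious harm would not simply go unseen.** Research assistants and nurses record events (6.4.1, 6.4.2), follow-up runs to one month after surgery (3.4), the data monitoring committee has unblinded access and the interim analysis covers secondary outcomes (3.3), and the principal investigator reviews adverse events (section 8). This is oversight of events, however, not a comparison between arms, and the stopping rule in 3.3 has no complication criterion.
- **Low power for secondary safety outcomes is usual**, especially in a trial that calls itself phase II. That is a reason to report intervals rather than rely on a test. Adding a second test would help little: 1% v 3% has 14% power with 100 per group (8% with 70).

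**Conclusion.** The concern holds for the pre-specified comparison. Safety is a named objective, its only planned analysis is a test for a difference, and the recorded severity has no analysis. A non-significant result could not support a statement of comparable safety: across the assumed rates, a 10-point rise in any complication is detected 24% to 52% of the time, and equal observed rates of 20% leave about ±11 points with 100 per group or ±13 with 70. The exact figures depend on assumed rates, but the conclusion is the same throughout the range. The documents do not support the stronger claim that the plan treats non-significance as proof of safety, or that an excess of serious events would escape the trial altogether. This should be changed; it does not invalidate the design.

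**What to change.** In sections 2.2.2 and 3.5:

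1. Report any complication, and each of pneumothorax, pulmonary hemorrhage and hemoptysis, by arm as a risk difference (template minus CT) with a 95% confidence interval: Newcombe, or an exact method where events are rare.
2. Tabulate the severity of pneumothorax and hemorrhage from the CT after localization, by arm, in categories fixed before analysis.
3. Base the safety statement on the upper limit of the interval, that is, the largest excess the data allow, and not on a p value. Unless an acceptable excess is specified beforehand, keep the conclusion descriptive.
4. Add complications that needed intervention as a further level only if the case report form records this.

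The cost is one more table and the work of defining severity categories. Sample size and procedures do not change. The downside is that the intervals will be wide, so the safety statement will look less favourable than a non-significant p value would.

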## **4 STYDT EBROLLMENT AND WITHDRAW**

### **4.1 Inclusion Criteria**

Patient scheduled lung nodule resection by VATS is assessed for eligibility.

The inclusion criteria are as follows.

- (1) The long-axis diameter of the target lung nodule is less than or equal to 20 mm;
- (2) The inner edge of the target nodule is at least 2 cm away from major pulmonary arteries or veins to allow secure nodule excision;
- (3) patient's surgeon in charge must confirm the necessity of preoperative lung nodule localization.
- (4) Male or female  $\geq 18$  years of age

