### **4.3 Treatment Assignment Procedures**

In order to randomly assign the participants to the two groups, a randomization list with 200 numbers was created using blocked randomization with a block size of 10. The 200 random numbers are each placed in sealed envelopes which are marked with sequential number at the cover.

Patients with scheduled lung resection are evaluated by research assistants. If the above criteria are met and patient's consent to participation has also been acquired, then the patient's information is sent to a person who is not involved with the trial by calling. Then, the accorded envelop is opened to assign the patient to template- or CT-guided localization group.

Because of the intrinsic property of the trial, no masking procedure is performed. After assignment, if the patient is allocated to template-guided lung nodule localization, research assistant needs to download the patients CT data from Picture Archiving and Communication Systems. The planned localization route is marked on CT images by patient's surgeon, then the CT data is emailed to designers for template design and printing. Because it takes about 6-8 hours for template production, all enrolled patents have to give consent to participate at least one day before the scheduled surgery.

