### **5.1 Control Group**

Patients in the CT-guided group received conventional CT-guided percutaneous lung nodule localization using a hookwire system. After patients were positioned on the examining table of the CT scanner (patient's position was decided based on the location of the target nodule), the initial CT scan was conducted through the area of interest using a slice thickness of 3 mm. The localizer insertion site was determined by the CT gantry laser lights and a metal marker on the skin. The insertion length and angle were measured on CT images, and the localizer was then inserted without penetrating the pleura. Afterwards, repeated CT scans were taken to confirm or redirect the localizer in order to obtain adequate accuracy of nodule localization. Based on previous experience, deviations of  $\leq 2$  cm between the localizer and the center of the target nodule were considered accurate enough to allow for safe nodule localization. After confirmation of accurate localizer placement, the practitioner inserted the localizer into

the lung parenchyma and removed the cannula of hookwire.

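### The primary comparison in Section 3.5 is unadjusted; prespecified adjustment for nodule diameter and baseline depth could add some precision, by an amount the documents do not let us know

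*Combined protocol and SAP*

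**What the plan says.** Section 3.5 (Statistical Analysis) lists three tests: independent-samples t "tests for continuous variables that were normally distributed", Mann-Whitney for other continuous variables, and chi-square for categorical ones. No covariate is named there or elsewhere. It adds "All statistical analyses are two-tailed with a significance level of 0.05".

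Section 3.2 sets the design: "The expected difference of localizer deviation between CT- and template-guided group was 3.5mm according to priori study"; "Deviation of 5mm is set as non-inferiority margin"; and "We needed to randomize 140 patients (70 each group) to give 90% power with one-sided alpha of 0.05". Enrolment is raised to 100 per arm for dropouts. No standard deviation is given.

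Section 4.3 describes blocks of 10 with no stratification factor.

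On size and path, three places matter:

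- Section 4.1 makes diameter an eligibility criterion: "The long-axis diameter of the target lung nodule is less than or equal to 20 mm".
- Section 5.1, for the CT arm during the procedure: "The insertion length and angle were measured on CT images".
- Section 4.3, for the template arm after assignment: "The planned localization route is marked on CT images by patient's surgeon".

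Neither depth nor path length is among the data to be recorded in Sections 2.2.2 and 6.

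**The concern.** The outcome is a distance in three dimensions from localizer to nodule centre, and both arms reach the nodule by choosing a skin site and an angle. It is plausible that some nodules are harder to hit than others for reasons visible on the CT before randomization. If so, an unadjusted comparison leaves that variation in the error term, and a chance imbalance between arms in size or depth stays in the estimate, since neither the randomization nor the analysis deals with it.

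At stake is the width of the interval to be set against 5 mm, and hence some power. The validity of the comparison is not in question.

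**Working it through.** **Inputs.** From Section 3.2: 70 per arm, 90% power, one-sided alpha 0.05, margin 5 mm. From Section 3.5: two-tailed 0.05, which for a non-inferiority limit acts as one-sided 0.025. R², the share of within-arm variance in deviation explained by diameter and depth, is not in the documents; I take 0 to 0.30 as an assumed range.

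**The plan's own figure.** Because no SD is stated, 70 per arm cannot be reproduced, only inverted. With g the distance from the true difference to the margin:

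SD = g × √(70/2) / (1.645 + 1.282)

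- True difference 0 (g = 5): SD = 10.11 mm.
- Template worse by 3.5 mm (g = 1.5): SD = 3.03 mm.
- Template better by 3.5 mm (g = 8.5): SD = 17.18 mm.

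Section 3.2 does not give the direction of the 3.5 mm, so the SD is open. The relative effect of adjustment does not depend on it: whichever SD is meant, 90% power at one-sided 0.05 fixes g/SE at 1.645 + 1.282 = 2.926 (unrounded quantiles).

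**Effect of adjustment.** The residual SD is SD × √(1 − R²), so

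power at 70 per arm = Φ(2.926/√(1 − R²) − z)

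with z = 1.645 or 1.960. For 100 per arm, 2.926 becomes 2.926 × √(100/70) = 3.498. The n for 90% power is 70 × (1 − R²), rounded up.

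| R² (assumed) | SE ratio | n per arm for 90%, one-sided 0.05 | Power, 70 per arm, 0.05 | Power, 70 per arm, 0.025 | Power, 100 per arm, 0.05 | Power, 100 per arm, 0.025 |
|---|---|---|---|---|---|---|
| 0 | 1.000 | 70 | 90.0% | 83.3% | 96.8% | 93.8% |
| 0.05 | 0.975 | 67 | 91.3% | 85.1% | 97.4% | 94.8% |
| 0.10 | 0.949 | 63 | 92.5% | 87.0% | 97.9% | 95.8% |
| 0.20 | 0.894 | 56 | 94.8% | 90.5% | 98.8% | 97.4% |
| 0.30 | 0.837 | 49 | 96.8% | 93.8% | 99.4% | 98.7% |

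Keeping all 100 per arm without adjustment gives the same power as R² = 0.30 with 70 per arm, because 70/100 = 1 − 0.30.

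**In millimetres.** At 70 per arm the distance from estimate to one-sided 95% limit is 1.645 × g/2.926. That is 2.81 mm at the SD of 10.11 and 0.84 mm at the SD of 3.03. R² = 0.10 multiplies each by 0.949, giving 2.67 mm and 0.80 mm.

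**Is there a common baseline measure?**

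- Diameter: yes. It must be known before randomization in both arms.
- Path length: no. In the CT arm it is measured on the table after assignment. In the template arm, Section 1.3.2 says the radiologist need not measure it, and the route is drawn after assignment, with no length stated as recorded.
- Depth on the earlier CT: not listed as collected, but obtainable. Sections 4.1 and 4.2 require the diameter, the distance from major vessels and the relation to the scapula, which are hard to judge without a chest CT. Section 4.3 shows that template-arm CT data are already in the archive after assignment. For the CT arm, availability is inferred from the shared eligibility criteria.

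**Would depth predict deviation?** A fixed angular error gives a miss of L × tan(angle). With an illustrative 5 degrees (assumption), that is 3.5 mm at 4 cm, 5.2 mm at 6 cm and 8.7 mm at 10 cm. This shows a mechanism; it is not evidence about R² in this trial.

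**The case against.** The strongest reply is that this is a preference. Randomization makes the unadjusted comparison valid without covariates, and chance imbalance is not bias. That stands.

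Three further objections have weight.

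- No section reports that deviation depends on depth or diameter. Section 1.1 links deep nodules to difficulty in recognizing them at surgery, which is another matter. The fixed-angle geometry also fits imperfectly: in Section 5.1 repeated scans allow the localizer to be redirected, and in Section 5.2 a checked deviation above 2 cm sends the patient to CT guidance. Both weaken any link with depth. For diameter no mechanism is evident. A reader might infer that the outcome scales with depth; the documents do not show it, so R² may be near zero.
- The geometry concerns needle path, whereas the proposed covariate is nodule depth, a proxy whose quality is unknown because the path depends on the chosen route and the patient's position.
- The plan never compares anything with 5 mm in Section 3.5. Supplying an interval for that purpose needs no covariates, so that benefit should not be credited to adjustment.

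A reader might also infer, from the measured insertion length in one arm and the marked route in the other, that path length is available for everyone and could be the covariate. It is not: both arise after assignment and by different processes, so assignment may affect them, and adjusting for them could distort the comparison.

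What remains is that a prespecified baseline covariate leaves the target, a mean difference in mm, unchanged and costs very little if it proves uninformative: at 70 per arm, two covariates reduce the residual degrees of freedom from 140 − 2 = 138 to 136.

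**Conclusion.** An optional improvement of low severity. The unadjusted analysis is valid and may forgo some precision; it should not be read as an error or a source of bias.

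The gain runs from nothing at R² = 0 to 6.8 percentage points of power at R² = 0.30 with 70 per arm and one-sided 0.05. At R² = 0.10 it is 2.5 points, equivalent to 7 patients per arm (70 − 63), and shrinks to 1.1 points if all 100 per arm complete. It is larger if the two-tailed 0.05 of Section 3.5 governs: 3.7 points at R² = 0.10 with 70 per arm.

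These figures rest on the assumed R², a normal approximation, equal SDs in the arms, and an SD equal to the one implied by the stated 90%. The case for depth also rests on the inference that a pre-randomization CT exists for every patient.

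**What to change.** In Section 3.5:

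1. Define the primary estimate as the template-minus-CT mean difference in deviation from a linear model with arm, nodule diameter and nodule depth, the last two taken from the pre-randomization CT.
2. Because deviation is a non-negative distance and may be skewed, use a robust or bootstrap interval and compare its upper limit with 5 mm. State its level, since Section 3.2 is one-sided 0.05 and Section 3.5 is two-tailed 0.05.
3. Keep the unadjusted mean difference with its interval as a sensitivity analysis.
4. State that insertion length or planned route length obtained after randomization is not used as a covariate.

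In Section 6, add depth to the recorded data with one written measurement rule, applied to both arms by someone unaware of the assignment. The rule should say which nodule counts if two are localized, since Section 4.2 excludes only more than two although Section 3.1 speaks of a solitary nodule.

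The cost is a few lines of text and one reading per patient from an archived CT, with no added procedure for patients. The downside is that small amount of data work, with little or no return if depth and diameter do not predict deviation.
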